5.7.4. Subgroup Analysis

Subgroup analyses of erythroid response will be performed with the following baseline factors, for NTD and TD patients separately:

- Age (< 32 and \geq 32 years)
- Sex (male and female)
- Prior iron chelation therapy (yes and no)
- Baseline LIC (< 3, 3-5, \geq 5 mg/g dw)
- Baseline EPO (< 200 and \geq 200 IU/L)
- Splenectomy (yes and no)
- Baseline iron intake (< 0.4 mg Fe/kg/day and \geq 0.4 mg Fe/kg/day)

- Baseline transfusion burden (RBC transfusion > 10 units per 12 weeks vs \leq 10 units per 12 weeks)

5.8. Safety Analysis

The safety endpoints will be summarized using the Safety Population. The safety endpoints include treatment emergent adverse events, changes in laboratory tests, vital signs and ECG's.

Severity of AEs will be coded using National Cancer Institute Common Toxicity Criteria for Adverse Events version 4.0 (NCI-CTCAE v4.0).

5.8.1. Adverse Events

For patients with treatment interruption, all non-serious AEs occurring after signing of the ICF until a patient is dosed on C1D1 are to be documented on the medical history CRF. All AEs and SAEs occurring after the Cycle 1 Day 1 dose through 56 days after the last study drug administration are to be reported and documented on the AE CRF. All AEs collected in this study are treatment emergent adverse events (TEAE). A drug-related TEAE is defined as any TEAE related to the study medication as assessed by the investigator or with missing assessment of the causal relationship.

The following summaries will be presented for all dosed:

- Number and percentage of patients reporting each AE, categorized by System Organ Class (SOC) and Preferred Term (PT)
- Number and percentage of patients reporting each AE experienced by $\geq 5\%$ and $\geq 10\%$ of patients in all patients by PT
- Number and percentage of patients reporting SAE, categorized by SOC and PT
- Number and percentage of patients reporting Grade ≥ 3 AE, categorized by SOC and PT
- Number and percentage of patients reporting related AE, categorized by SOC and PT
- Number and percentage of patients reporting AE leading to drug withdrawal, categorized by SOC and PT
- Number and percentage of AE of interests by cycle

Note that counting will be by patient, not event, and patients are only counted once within each SOC or PT. If a patient experiences the same AE at more than one severity, or with more than one relationship to study drug, the most severe rating or the stronger causal relationship to study drug will be given precedence. Any missing severity, causality, or outcome will not be imputed and classed as unknown.

All AEs will be listed. The following listings will also be provided: 1) patients with SAEs; 2) patients with Grade ≥ 3 AEs; and 3) patients with AEs leading to study drug discontinuation; 4) death.

Concomitant medication use, severity, time to the worst CTCAE grade and recovery will be listed and summarized.

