11.3. Other Safety Assessments

- Physical examination (including optional evaluation of gonadal size in males at specified timepoints)
- Vital signs: weight, heart rate, systolic and diastolic blood pressure.
- 12-lead ECG
- ADA testing: (Blood samples should be drawn and processed on-site for serum collection at the time points specified according to the relevant Laboratory Manual)
- The occurrence of a new malignancy or premalignant lesion will be monitored as an event of interest and should be included as part of the assessment of adverse events throughout the course of the study. Investigators are to report the development of any new malignancy or premalignant lesion as a serious adverse event, regardless of causal relationship to study drug, occurring at any time for the duration of the study, from the time of signing the ICF up to and including 3 years of follow up.

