- Is an important medical event: an important medical event is an event that may not result in death, be life-threatening, or require hospitalization but may be considered an SAE when, based upon appropriate medical judgment, it may jeopardize the patient and may require medical or surgical intervention to prevent one of the outcomes listed in the definitions for SAEs. Examples of such medical events include

allergic bronchospasm requiring intensive treatment in an emergency room or at home, blood dyscrasias or convulsions that do not result in inpatient hospitalization, or the development of drug dependency or drug abuse.

For the purposes of reporting, any suspected transmission of an infectious agent via a medicinal product is also considered a serious adverse reaction and all such cases should be reported in expedited manner.

Events Not to Be Considered as Serious Adverse Events

Elective hospitalizations to administer or to simplify study treatment or procedures are not considered SAEs.

Adverse Events of Special Interest

Events of new malignancy and premalignant lesions (excluding benign tumors or benign neoplasia) are to be reported as described in [Section 14.7](#) within 24 hours of the investigator's knowledge of the event by fax, or other appropriate method, using the SAE Report Form, and must be considered an "Important Medical Event" even if no other serious criteria apply; these events must also be documented in the appropriate page(s) of the CRF and subject's source documents. Documentation of the diagnosed malignancy must be provided at the time of reporting as a serious adverse event (e.g., any confirmatory histology or cytology results, X-rays, CT scans, etc.).

Malignancies or cancerous tumors are lesions capable of invading into adjacent tissues, and may be capable of spreading to distant tissues. A benign tumor has none of those properties.

Malignancy or cancer is characterized by anaplasia, invasiveness, and metastasis.

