Premalignant or precancerous lesions refer to a state of disordered morphology of cells that is associated with an increased risk of cancer. If left untreated, these conditions may lead to cancer. Such conditions are usually either dysplasia or benign neoplasia (and the dividing line between those is sometimes blurry). Sometimes the term "precancer" is used to describe carcinoma in situ, which is a noninvasive cancer that has not progressed to an aggressive, invasive stage. Not all carcinoma in situ will progress to invasive disease.

Premalignant lesions are morphologically atypical tissue which appears abnormal under microscopic examination and in which cancer is more likely to occur than in its apparently normal counterpart.

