14.5.1. Documentation of Serious Adverse Events

All SAEs that occur after the first study drug administration on Cycle 1 Day 1 until 56 days after the last study drug administration (EOS visit) are to be documented on the AE CRF. SAEs should not be reported for patients who are considered screen failures unless the event is deemed due to a protocol required procedure.

For all SAEs, an SAE form must be completed with as much information as possible and submitted within the time frame described in [Section 14.7](#).

When new significant information is obtained as well as when the outcome of an event is known, the investigator should record the information on a new SAE form. If the patient was hospitalized, a copy of the discharge summary must be included as part of the patient medical file. In all instances, the investigator should follow up with patients until the outcome of the SAE is known.

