14.6. Reporting Period and Monitoring of Patients with Adverse Events

As described in [Section 14.5](#), all AEs must be recorded in the CRF up until the end of the treatment period. All patients who took at least one dose of study drug, whether they completed the treatment period or not, should complete the end of treatment procedures.

All AEs will be followed until clinical database lock (or resolution if it occurs before database lock). All SAEs will undergo active follow up until resolved or the event becomes chronic or stable. Follow up data for SAEs obtained after clinical database lock will be incorporated into the ACE-536 safety database.

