5.8.6. Post-treatment Follow-up and Long-term Follow-up

A listing of post-treatment follow-up and Long-term follow-up data including the visit date, malignancy status, and survival status will be provided.

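### Malignancy, the protocol's only named event of special interest, has conflicting capture windows and case definitions, and the SAP plans no incidence summary for the 3-year follow-up

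*SAP*

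**What the plan says.** **Role of the event.** New malignancy or premalignant lesion is the only entry under the special-interest heading in Protocol 14.1. Such a lesion must always be handled as serious, on the SAE form and in the CRF. Footnote 27 of the protocol's Schedule of Events gives monitoring for these lesions as the purpose of the six-monthly long-term follow-up (LTFU) visits.

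**Capture window.**
- Protocol 11.3 requires these lesions to be reported as SAEs "from the time of signing the ICF up to and including 3 years of follow up".
- Protocol 14.5.1 says that SAEs from the first dose "until 56 days after the last study drug administration (EOS visit) are to be documented on the AE CRF". Section 14.5 sets the same limit for all AEs. Neither makes an exception for malignancy.
- Protocol 14.6, while referring back to 14.5, says that "all AEs must be recorded in the CRF up until the end of the treatment period".
- SAP 5.8.1 takes over the 56-day limit.

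**End-of-study visit.** Schedule footnote 28, Protocol 12.6 and SAP 5.1 place EOS about 3 years after the last dose. Sections 14.5 and 14.5.1 attach the EOS label to day 56. Protocol 9.4 and SAP 3.2 place EOS about 28 days after the end-of-treatment (EOT) visit for patients who stop early. Footnote a in Protocol 10.8 sends patients who stop after repeated AE-driven dose reductions through EOT, post-treatment follow-up, LTFU and EOS.

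**Case definition.** Protocol 14.1 first states: "Events of new malignancy and premalignant lesions (excluding benign tumors or benign neoplasia) are to be reported". Its description of premalignant lesions then says: "Such conditions are usually either dysplasia or benign neoplasia".

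**Analysis.** SAP 5.8.1 plans tables of all AEs, SAEs, Grade 3 or higher AEs and related AEs by SOC and PT, and one further output: "Number and percentage of AE of interests by cycle". It treats every AE collected in the study as treatment emergent. For the follow-up period, SAP 5.8.6 says: "A listing of post-treatment follow-up and Long-term follow-up data including the visit date, malignancy status, and survival status will be provided".

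**The concern.** A 5-year extension study with 3 further years of observation should be able to say how many patients developed a new malignancy or premalignant lesion, over how much observed time, and whether this happened on or after treatment. The plan does not secure any of the three. The SAP does not name malignancy among its safety endpoints in 5.8, the events-of-interest category has no definition, and a by-cycle layout has no place for an event after the last cycle.

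The protocol text adds to this, because sites can differ on how long to report and on which lesions qualify. The count behind any statement on malignancy could then depend on which sentence each site and the programmer followed. A by-cycle table with no cases could also stand beside listed follow-up cases that no one had counted.

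**Working it through.** **1. The plan's own time figures.** There is no formal sample size to reproduce. Maximum participation is 1 + 60 + 36 = 97 months, as stated. Cycle 87 Day 1 falls on day 1 + 86 × 21 = 1807, as in the schedule.

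**2. The windows side by side.**

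| Source | Starts | Ends |
|---|---|---|
| Protocol 11.3 (malignancy, as SAE) | consent | 3 years of follow-up |
| Protocol 14.5, 14.5.1; SAP 5.8.1 | first dose on Cycle 1 Day 1 | last dose + 56 days |
| Protocol 14.6 | (refers to 14.5) | end of treatment period |

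These cannot all apply to one lesion found, say, 2 years after the last dose.

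**3. Where that lesion goes in the SAP.**
- If the 56-day limit governs, it is not on the AE CRF. It appears in the 5.8.6 listing and is not counted.
- If Protocol 11.3 governs, it is a collected SAE. SAP 5.8.1 then calls it treatment emergent and counts it in the SAE table by SOC and PT, together with on-treatment events and with no time split.
- In neither case does it have a place in a by-cycle table, or a person-time denominator.

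**4. Time at stake.** Inputs: 64 patients (SAP 3.3), 5 years of treatment, 3 years of follow-up, 56-day limit. Assumption: every patient completes both periods. A year is 365.25 days.
- Treatment: 64 × 5 = 320 person-years.
- First 56 days after treatment: 64 × 56 / 365.25 = 9.8 person-years, giving 329.8 in total.
- Day 56 to 3 years: 64 × (1095.75 − 56) / 365.25 = 182.2 person-years.
- Share after day 56: 182.2 / (329.8 + 182.2) = 182.2 / 512.0 = 36%.
- Share of each patient's follow-up after day 56: 1039.75 / 1095.75 = 95%.

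**5. Sensitivity.**
- SAP 4.1 adds A536-04 data for direct rollovers. At up to 3 months each this is at most 64 × 0.25 = 16 person-years, and the share becomes 182.2 / 528.0 = 35%.
- Protocol 15.3 gives 72 patients instead of 64. The person-years after day 56 become 72 × 1039.75 / 365.25 = 205, and the share does not change.
- A patient who stops early and has EOS about 28 days after EOT contributes roughly nothing after day 56. Each such patient removes 1039.75 / 365.25 = 2.85 person-years. With 64 patients the amount therefore lies between 0 and 182 person-years, depending on how many stop early and which EOS rule is followed.

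**6. Case definition.** The reporting sentence in 14.1 removes benign neoplasia. The descriptive paragraph says of premalignant conditions: "Such conditions are usually either dysplasia or benign neoplasia (and the dividing line between those is sometimes blurry". The same term is thus on both sides of the boundary, and the text itself concedes that the boundary is unclear.

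**The case against.** A reader might infer that follow-up malignancies reach no summary table at all. The documents do not support that. Protocol 11.3 and 14.1 require these lesions as SAEs in the CRF, and SAP 5.8.1 has an SAE table that is not by cycle and sets no date limit on treatment emergence. A case recorded under 11.3 could be counted there. It drops out only if the general 56-day sentence overrides the specific malignancy rule, and the documents do not say which prevails. Malignancies inside the 56-day window would appear in the SOC and PT tables in any case.

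Four further points have weight.
- The SAP never says that its events of interest are malignancies. The link is inferred from the protocol, so the firm criticism is that the category is undefined.
- The events are not lost. The schedule has a dedicated monitoring row and SAP 5.8.6 lists malignancy status.
- In a descriptive single-arm study of at most 64 patients by the SAP's count, a listing shows every case.
- The descriptive paragraph in 14.1 is background and hedged. It does not instruct sites both to exclude and to report the same lesion.

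What survives is this. A listing gives neither a patient count nor a denominator. The SAE table, if it takes in follow-up cases, spreads them over SOC and PT rows and mixes them with on-treatment events. The conflicting windows and the two uses of benign neoplasia stand in the current text whichever reading is preferred.

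**Conclusion.** The point holds in this form: the window and the definition for the protocol's only named event of special interest are contradictory, and the SAP plans no incidence summary for the period set aside to detect it. A follow-up case is either uncounted or pooled as treatment emergent, and the documents do not determine which. It would be wrong to say that such cases certainly go unsummarised, or that a fixed share of follow-up lies outside every table.

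About 182 of 512 person-years (36%) fall after day 56 if all 64 patients complete 5 years of treatment and 3 years of follow-up. The 182 is an upper limit for 64 patients, and it shrinks if early discontinuers leave at the EOS visit described in Protocol 9.4 and SAP 3.2. Because the primary objective is long-term safety, this should be settled before database lock. Lesions that a site did not report under its reading of the protocol cannot be fully recovered later.

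**What to change.** **SAP 5.8.1 and 5.8.6.** Define the events-of-interest category. Add one table of patients with at least one new malignancy or premalignant lesion, combining AE CRF, SAE and LTFU records. Run it from the first ACE-536 dose (the first A536-04 dose for direct rollovers) to EOS, split at last dose plus 56 days, with person-years in each part. State whether follow-up cases also enter the SAE table by SOC and PT.

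**Protocol 14.5, 14.5.1 and 14.6.** Reconcile these to one AE end date, carry the 11.3 malignancy window as an explicit exception, and correct the EOS label attached to day 56. Reconcile Protocol 9.4 and SAP 3.2 with schedule footnotes 27 and 28, footnote a in 10.8, and 12.6, so that the follow-up expected of early discontinuers is stated once.

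**Protocol 14.1.** Reconcile the two statements on benign neoplasia. The choice of definition is for the sponsor and its clinical advisers.

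**Cost.** One extra table, built from records the plan already provides for, and minor wording changes. No change to the design is needed.

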5.8.2. Laboratory Evaluations

The following laboratory parameters will be measured over time:

Hematology:

RBC, white blood cell (WBC) with differential, hemoglobin, hematocrit, haptoglobin (optional), reticulocyte count, platelet count, mean corpuscular volume (MCV), mean corpuscular hemoglobin (MCH), mean corpuscular hemoglobin concentration (MCHC), red blood cell distribution width (RDW), and nucleated RBCs (nRBCs).

Chemistry:

Sodium, potassium, chloride, carbon dioxide/bicarbonate (optional), aspartate aminotransferase (AST), alanine aminotransferase (ALT), lactate dehydrogenase (LDH), total bilirubin, indirect bilirubin, alkaline phosphatase, blood urea nitrogen (BUN)/urea, creatinine, gamma-glutamyl transpeptidase (GGT), calcium, phosphorus, glucose, amylase, lipase, total protein, albumin, and uric acid.

Urine Analysis:

Local lab dipstick analysis will be done for specific gravity, protein, glucose, ketones, blood, leukocyte esterase, and nitrite, with microscopic examination if performed.

Urine Chemistry:

Microalbumin and creatinine will be performed by the central lab; albumin/creatinine ratio will be provided.

Categorical and numeric variables will be presented separately. Actual values and changes in hematology and biochemistry laboratory values from baseline will be summarized by time point. Shift tables for the hematology and biochemistry laboratory parameters comparing values above, within and below the normal reference range at baseline to the end of treatment visit will be presented using standard reference ranges.

Actual urine laboratory values will be listed.

Peripheral blood smears data will be listed only. All laboratory values will be listed for all patients.

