- 6 **Vital signs** will include weight, heart rate, and SBP and DBP. If at any visit the systolic blood pressure is ≥ 150 mmHg, the diastolic blood pressure is ≥ 95 mmHg and/or the absolute increase in either measure from baseline is ≥ 20 mmHg, perform one repeat of the blood pressure assessment after a minimum of 15 minutes.
- 7 **MRI for liver iron content** will be performed at selected sites at C1D1, C9D1 C17D1, C25D1, C33D1, C41D1, C49D1, C57D1, C65D1, C73D1, C81D1 and EOT within a +/- 10-day window for each scan. A MRI for liver iron content is not required if < 3 months since the previous MRI for liver iron content, unless clinically indicated.
- 8 **MRI of the chest and abdomen for EMH mass measurement** will be performed for at selected sites at C1D1. If the assessment at C1D1 is negative (no masses), additional scans are not required unless clinically indicated. If the assessment at C1D1 is positive (masses present), repeat MRI at C9D1, C17D1, C25D1, C33D1, C49D1, C65D1, C81D1 and EOT within a +/- 10-day window for each scan. A MRI of the chest and abdomen for EMH mass measurement is not required if < 3 months since the previous MRI of the chest and abdomen for EMH mass measurement, unless clinically indicated.
- 9 **MRI of the spleen:** will be performed at selected sites at C1D1 on patients with no prior splenectomy. If there is no indication of an enlarged spleen on the C1D1 scan, additional scans are not required unless clinically indicated. If there is an enlarged spleen on the C1D1 scan, repeat imaging at C9D1 C17D1, C25D1 C33D1, C49D1, C65D1, C81D1 and EOT within a +/- 10-day window for each scan. Patients with clinical signs of a change in spleen size or abnormality should have an abdominal ultrasound or MRI performed as needed throughout the study. A MRI for the spleen is not required if < 3 months since the previous MRI for the spleen, unless clinically indicated.
- 10 **Leg ulcer assessment:** Patients with leg ulcers should have regular assessment of the leg ulcer(s) throughout the study. Photographs of the leg ulcer(s) pre- and post- dose should be provided when available to document any changes in the ulcer(s).
- 11 **Serum iron studies:** May include serum iron, TIBC, transferrin, soluble transferrin receptor, calculated transferrin saturation, ferritin, NTBI. The sponsor may perform additional sample analysis for biomarkers for exploratory research purposes only.

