7.4. Potential Risks of Human Use

Increases in hematologic parameters (RBC, hemoglobin, hematocrit, reticulocytes) are expected pharmacologic effects of ACE-536 treatment. Increases in systolic and diastolic blood pressures may occur in concert with increases in hemoglobin values. Excessive or rapid increases in hemoglobin or blood pressure may occur and will be monitored. Dose modifications rules for individual patients and dose escalation/reduction rules will be utilized to minimize risks associated with increased RBC parameters.

AEs observed in the Phase 1 study in healthy volunteers and the ongoing phase 2 studies that were considered probably or possibly related to study drug included injection site reactions (hemorrhage, pruritus, rash), skin rash, hyperesthesia, muscle spasms, myalgia, pruritus, and hyperkalemia.

As with all biologics, there is the potential for anti-drug antibodies (ADA) that can be associated with increased drug clearance and hypersensitivity reactions. ADA formation against ACE-536 as well as human ActRIIB protein will be monitored in the initial clinical studies.

Repeat-dose toxicology studies of 1 and 3 month treatment duration have been conducted with ACE-536 in Sprague-Dawley rats and cynomolgus monkeys to evaluate the toxicity of ACE-536. In addition, the main phase of a repeat-dose toxicology study of 6 months treatment duration in cynomolgus monkeys is complete. Reproductive toxicity studies are currently ongoing with ACE-536 and therefore ACE-536 should not be administered to pregnant or nursing women. Male and female subjects of childbearing potential participating in studies of ACE-536 must be willing to abstain from sexual intercourse or use adequate contraception during treatment and for at least 12 weeks following the last dose of ACE-536. Please refer to the Investigator’s Brochure for additional information regarding findings from toxicology studies. It is unknown if humans will experience any of the effects of ACE-536 that were noted in the rat and monkey toxicology studies. Safety effects will be monitored closely through AE reporting, clinical laboratory tests, vital signs, and physical examinations. A comprehensive review of ACE-536, as well as details regarding the information summarized above, is provided in the IB. The ACE-536 IB should be reviewed prior to initiating the study.

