15.2.2. Primary Endpoint Analysis

To assess clinical safety, all AEs, vital sign measurements and clinical laboratory information will be summarized. AEs will be coded using the Medical Dictionary for Regulatory Activities (MedDRA). Changes from baseline for clinical laboratory values and vital signs will be summarized over time. Descriptive statistics and shift tables will be generated as appropriate. Disposition rates will be summarized.

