5.8.3. Vital Signs

Vital signs parameters include weight (kg), heart rate, systolic and diastolic blood pressure, respiratory rate, and temperature (°C). For each parameter at each time point, the change from baseline to post baseline will be summarized.

Plots of vital sign parameters for both mean observed and mean change from baseline will be presented for each parameter. Vital signs will also be listed for all patients.

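### The SAP only lists urine laboratory results where the protocol promises summaries, and it plans no count of patients who cross the protocol's own blood pressure thresholds

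*SAP*

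**What the plan says.** **Urine.** Protocol 15.2.2, on the primary (safety) endpoint, states: "Changes from baseline for clinical laboratory values and vital signs will be summarized over time". The next sentence adds: "Descriptive statistics and shift tables will be generated as appropriate". SAP 5.8 also names changes in laboratory tests among the safety endpoints to be summarised.

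SAP 5.8.2 has separate entries for hematology, chemistry, urine analysis and urine chemistry. Under urine chemistry it says: "Microalbumin and creatinine will be performed by the central lab; albumin/creatinine ratio will be provided". Its summary rule is: "Actual values and changes in hematology and biochemistry laboratory values from baseline will be summarized by time point". Shift tables are confined to the same two groups. The rule for urine is: "Actual urine laboratory values will be listed".

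Protocol 15.5 says that the SAP will indicate deviations from the protocol's analyses. SAP 5.12.6 records two: the definition of baseline hemoglobin, and the removal of the efficacy evaluable population together with the renaming of mITT.

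**Blood pressure.** Protocol 7.4 warns: "Excessive or rapid increases in hemoglobin or blood pressure may occur and will be monitored". The vital-signs footnote in protocol section 2 asks for a second reading when SBP is 150 mmHg or more, when DBP is 95 mmHg or more, or when "the absolute increase in either measure from baseline is ≥ 20 mmHg, perform one repeat of the blood pressure assessment". Protocol 12.1 to 12.3 repeat this. SAP 5.8.3 says: "For each parameter at each time point, the change from baseline to post baseline will be summarized". It adds plots of means and a patient listing. By SAP 5.2, a summary of continuous data gives n, mean, SD, minimum, median and maximum.

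**The concern.** Long-term safety is the primary objective, so the safety tables are the main result of the study. The albumin/creatinine ratio is a numeric result measured repeatedly over up to 60 months. A listing gives no average, spread or change at any time point, so a reader would have to build the summary that the protocol promised.

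The blood pressure gap is of a different kind. The protocol names the risk and sets thresholds at which a reading is checked, but no SAP analysis uses them. Statistics computed visit by visit cannot say how many patients were ever affected. A visit that triggers the check also produces two readings, and with no rule on which one is analysed, the summaries depend on a programming choice.

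**Working it through.** The study is descriptive and has no sample size calculation, so there is no planned figure to reproduce. The check is a comparison of texts, followed by an illustration.

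**1. Is urine exempt from the protocol's promise?** The sentence in protocol 15.2.2 on changes from baseline covers clinical laboratory values without exception. The words *as appropriate* stand in the following sentence and govern the type of table. The protocol makes no exemption.

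**2. Could *biochemistry* in SAP 5.8.2 include urine chemistry?** This is unlikely. The section gives chemistry and urine chemistry separate headings, and urine has its own listing sentence.

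**3. Is the departure recorded?** No. Neither entry in SAP 5.12.6 concerns urine.

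**4. How often is urine collected?** By the schedule of events: C1D1 (1), every fourth cycle from C5 to C17 (4), one visit in each four-cycle block from C20–23 to C84–87 (17), and EOT (1). The total is 1 + 4 + 17 + 1 = 23 per patient for someone who completes treatment.

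**5. What do the planned blood pressure statistics show?** Inputs: N = 64 (SAP 3.3; protocol 15.3 says 72). Assumption, not from the documents: k patients rise by 25 mmHg at a visit and the others do not change. Then

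- mean change = 25k/N
- SD = √[(k·25² − N·mean²)/(N − 1)]

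With k = 5 and N = 64:

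- mean = 125/64 = 1.95 mmHg
- SD = √[(3,125 − 244.1)/63] = 6.8 mmHg
- median 0, maximum 25

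With N = 72 the mean is 125/72 = 1.74 mmHg. A threshold table would instead report 5/64 = 7.8% (exact 95% CI 2.6 to 17.3).

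Varying k with N = 64:

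| k | Mean (mmHg) | SD (mmHg) | Median | Maximum | Patients, % (exact 95% CI) |
|---|---|---|---|---|---|
| 1 | 0.4 | 3.1 | 0 | 25 | 1.6 (0.04–8.4) |
| 5 | 2.0 | 6.8 | 0 | 25 | 7.8 (2.6–17.3) |
| 10 | 3.9 | 9.1 | 0 | 25 | 15.6 (7.8–26.9) |

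The median and maximum do not change from 1 patient to 10. The mean and SD do move, but in real data they mix such patients with ordinary variation.

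**6. Can visits be joined up?** Suppose 5 patients rise at each of four visits. If they are the same patients, 5 of 64 (7.8%) were ever affected. If they are different patients each time, 4 × 5 = 20 of 64 (31.3%) were. The four per-visit tables are identical in the two cases.

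**7. Which reading is analysed?** SAP 5.1 takes the last observation on or before C1D1 as baseline, which points to the repeat reading there. SAP 5.8.3 gives no rule after baseline, and SAP 5.12.1 leaves window rules to the programming specifications.

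**The case against.** The strongest reply is that blood pressure is not reduced to means. SAP 5.2 adds SD, minimum, median and maximum, and all values are listed. In the illustration, a reader of the planned table would see the maximum of 25 mmHg. The protocol promises only that vital-sign changes be summarised over time, and the SAP does that. All of this stands: the blood pressure half is a weakness in the analysis and not a contradiction.

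The thresholds trigger a repeat reading and are not endpoints. They also differ from the uncontrolled-hypertension limits in exclusion criterion 11 (SBP ≥150 or DBP ≥100 mmHg). That is fair, but they are the protocol's own on-study markers of a reading that needs checking, so using them brings in no outside cut-off.

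An ever-crossed count also grows with the number of visits. Suppose changes are normal with mean zero and SD 10 mmHg (an assumption). The chance of a rise of 20 mmHg or more at one visit is then 0.0228. Over 87 post-baseline visits (C2 to C87 and EOT) that gives 87 × 0.0228 = 2.0 expected crossings per patient. For SD 8 and 12 the figures are 87 × 0.0062 = 0.5 and 87 × 0.0478 = 4.2. This is a good reason to show the confirmed count beside the first-reading count; it does not justify showing neither.

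A reader might infer that these two measures yield no usable safety result. The documents do not support that. Clinically relevant findings are recorded as adverse events and counted by preferred term (protocol 14.5, SAP 5.8.1), and the safety review team looks at laboratory results and vital signs (protocol 10.6). Serum creatinine and BUN are in the chemistry panel, which gets change summaries and shift tables. The adverse event route is incomplete, because protocol 14.1 leaves out abnormal findings that are not symptomatic, do not lead to discontinuation and are not judged clinically relevant.

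A reader might also infer that the urine ratio is a known renal signal. Protocol 7.4 names blood pressure but no renal risk.

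Finally, SAP 5.12.6 claims to list only major changes, and whether this one is major is a judgement. Protocol 15.5 carries no such qualifier.

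**Conclusion.** The point holds in two parts of unequal weight.

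- **Urine:** the SAP replaces a promised summary with a listing and does not say so. This rests on the texts alone. Multiplying 23 collections by 64 patients gives 1,472 listed values, but that is a volume of data under full completion and not a measure of harm or bias.
- **Blood pressure:** the protocol's promise is met. Yet no planned table gives the number of patients who ever cross the protocol's thresholds for a named risk, and the reading to be analysed is not specified. The shift of about 2 mmHg in the mean depends on the assumed 5 patients and 25 mmHg and shows only what the per-visit statistics can and cannot reveal. How far the choice of reading would move the results cannot be estimated from the documents.

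Both parts are worth correcting before database lock, because they concern the primary objective and the data already exist. Neither invalidates the safety analysis.

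**What to change.** In SAP 5.8.2, add the urine albumin/creatinine ratio to the summary of actual values and change from baseline by time point. If urine is to stay as a listing, record and justify that in SAP 5.12.6. A table of ratio categories is not requested, because neither document gives cut-offs.

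In SAP 5.8.3, add the number and percentage of patients, with exact 95% CI, who ever meet each protocol threshold after baseline (SBP ≥150 mmHg, DBP ≥95 mmHg, rise ≥20 mmHg). Give this once on the first reading and once confirmed on the repeat. State one pre-specified rule for which reading enters the by-visit summaries, and say whether the same rule applies at baseline.

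The cost is two or three more descriptive tables from data already collected. No visit, measurement or clinical rule changes.
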